## Appendix A: Terms and Definitions

For the purposes of this protocol the following terms and definitions apply.

Term	Definition
Adverse Device Effect (ADE)	
Any untoward and unintended response to a medical device. This includes Serious Adverse Device Effects and any event resulting from insufficiencies or inadequacies in the instructions for use or the deployment of the device, and any event resulting from a user error.
 
Note 1: This definition includes adverse events resulting from insufficient or inadequate instructions for use, operation, or any malfunction of the investigational medical device.
 
Note 2: This definition includes any event resulting from use error or from intentional misuse of the investigational medical device.
 
ISO 14155:2011

Adverse Event (AE)	
Any untoward medical occurrence, unintended disease or injury, or untoward clinical signs (including abnormal laboratory findings) in subjects, users or other persons, whether or not related to the investigational medical device.
 
Note 1: This definition includes events related to the investigational medical device or the comparator.
 
Note 2: This definition includes events related to the procedures involved.
 
Note 3: For users or other persons, this definition is restricted to events related to investigational medical devices.
 
Note 4: Severity of AEs defined in section 12.1 for reference
 
21CFR312.32, ISO 14155:2011

Adverse Events of Special Interest	
Adverse Events that relate to the Endpoints
 
 
• sICH up to 90 days
 
• aICH up to 24 hour timepoint
 
• Any AE at least possibly related to procedure or device
 
• Neurological deterioration up to 7 days or discharge (whichever is earlier)
 
• All-cause mortality (including stroke-related and procedure-related mortality)
 

All-cause Mortality	The term is utilized for death from any cause.
Asymptomatic ICH (aICH)	
New intracranial hemorrhage that has no implications for prognosis or change in management, and there is no substantive change in the patient's neurological status as defined by the Heidelberg Bleeding Classification.
 
See Heidelberg Bleeding Classification for additional criteria.

As-Treated population	The As-Treated population is a subset of the ITT population that and will consist of all subjects randomized into the study analyzed according to the treatment received.
Audit	Systematic independent examination of activities and documents related to clinical investigation to determine whether these activities were conducted,

	and the data recorded, analyzed and accurately reported, according to the Protocol, standard operating procedures, this International Standard and applicable regulatory requirements.				
Clinical Investigation	Systematic investigation in one or more human subjects, undertaken to assess the safety or performance of a medical device.  Note1: "Clinical trial" or "clinical study" are synonymous with "clinical investigation".				
Clinical Protocol	Document that state(s) the rationale, objectives, design and proposed analysis, methodology, monitoring, conduct and record-keeping of the clinical investigation.				
Clinical Investigation Report	Document describing the design, execution, statistical analysis and results of a clinical investigation.				
Clinical Performance	Behavior of a medical device or response of the subject(s) to that medical device in relation to its intended use, when correctly applied to appropriate subject(s).				
Contract Research Organization (CRO)	Person or organization contracted by the sponsor to perform one or more of the sponsor's clinical investigation-related duties and functions.				
Control Device	Reference Section 6.2 (Table 6.1)				
Coordinating Investigator	Investigator who is appointed by the sponsor to coordinate work in a multicenter clinical investigation.				
Data Monitoring Committee (DMC)	Independent committee established by the sponsor to assess, at intervals, the progress of the clinical investigation, the safety data or the critical performance endpoints and to recommend the sponsor whether to continue, suspend, modify, or stop the clinical investigation.				
Deviation	See Protocol Deviation				
Device Deficiency	Inadequacy of a medical device with respect to its identity, quality, durability, reliability, safety or performance.  NOTE Device deficiencies include malfunctions, use errors, and inadequate labelling.				
Device-related or procedure-related symptomatic intracranial hemorrhage (sICH)	sICH adjudicated by the CEC to be related to therapeutic intervention (either definite or probable) as defined by the Heidelberg Bleeding Classification.				
Early Response	A NIHSS drop of $\geq 10$ points from baseline or NIHSS score 0 or 1				
Enrolled	All consecutive patients with a signed Informed Consent Form (ICF) will be considered part of the enrolled population.				
eTICI	Refers to the expanded Thrombolysis in Cerebral Infarction scale.  
 
 Score/Grade	Criteria	
 
 0	No reperfusion	
 
	Score/Grade	Criteria	0	No reperfusion
Score/Grade	Criteria				
0	No reperfusion				

	

1	Reduction in thrombus without filling of distal arterial branches	

2a	Reperfusion in less than half the territory	

2b50	Reperfusion in 50–66% of the territory	

2b67	Reperfusion in 67–89% of the territory	

2c	Extensive reperfusion in 90–99% of the territory	

3	Complete or full reperfusion	

	1	Reduction in thrombus without filling of distal arterial branches	2a	Reperfusion in less than half the territory	2b50	Reperfusion in 50–66% of the territory	2b67	Reperfusion in 67–89% of the territory	2c	Extensive reperfusion in 90–99% of the territory	3	Complete or full reperfusion																											
1	Reduction in thrombus without filling of distal arterial branches																																							
2a	Reperfusion in less than half the territory																																							
2b50	Reperfusion in 50–66% of the territory																																							
2b67	Reperfusion in 67–89% of the territory																																							
2c	Extensive reperfusion in 90–99% of the territory																																							
3	Complete or full reperfusion																																							
The Heidelberg Bleeding Classification	The Heidelberg Bleeding Classification is a process to categorize intracranial hemorrhage into sICH or aICH based on both a pure radiological classification scheme and a combined radiological-symptomatic classification scheme. This process is detailed in von Kummer R et al. 																																							
Informed consent process	Process by which an individual is provided information and is asked to voluntarily participate in a clinical investigation.  Note 1: Informed consent is documented by means of a written, signed and dated informed consent form.																																							
Intracranial Hemorrhage	
Defined per the Heidelberg Bleeding Classification
 

Anatomic Description of Intracranial Hemorrhages	

Class	Type	Description	

1		Hemorrhagic transformation of Infarcted brain tissue	

1a	HI1	Scattered small petechiae, no mass affect	

1b	HI2	Confluent petechiae, no mass effect	

1c	PH1	Hematoma within infarcted tissue, occupying <30%, no substantive mass effect	

2		Intracerebral hemorrhage within and beyond infarcted brain tissue	

	PH2	Hematoma occupying 30% or more of the Infarcted tissue, with obvious mass effect	

3		Intracerebral hemorrhage outside the infarcted brain tissue or Intracranial-extracerebral hemorrhage	

3a		Parenchymal hematoma remote from infarcted brain tissue	

3b		Intraventricular hemorrhage	

3c		Subarachnoid hemorrhage	

3d		Subdural hemorrhage	

	Anatomic Description of Intracranial Hemorrhages			Class	Type	Description	1		Hemorrhagic transformation of Infarcted brain tissue	1a	HI1	Scattered small petechiae, no mass affect	1b	HI2	Confluent petechiae, no mass effect	1c	PH1	Hematoma within infarcted tissue, occupying <30%, no substantive mass effect	2		Intracerebral hemorrhage within and beyond infarcted brain tissue		PH2	Hematoma occupying 30% or more of the Infarcted tissue, with obvious mass effect	3		Intracerebral hemorrhage outside the infarcted brain tissue or Intracranial-extracerebral hemorrhage	3a		Parenchymal hematoma remote from infarcted brain tissue	3b		Intraventricular hemorrhage	3c		Subarachnoid hemorrhage	3d		Subdural hemorrhage
Anatomic Description of Intracranial Hemorrhages																																								
Class	Type	Description																																						
1		Hemorrhagic transformation of Infarcted brain tissue																																						
1a	HI1	Scattered small petechiae, no mass affect																																						
1b	HI2	Confluent petechiae, no mass effect																																						
1c	PH1	Hematoma within infarcted tissue, occupying <30%, no substantive mass effect																																						
2		Intracerebral hemorrhage within and beyond infarcted brain tissue																																						
	PH2	Hematoma occupying 30% or more of the Infarcted tissue, with obvious mass effect																																						
3		Intracerebral hemorrhage outside the infarcted brain tissue or Intracranial-extracerebral hemorrhage																																						
3a		Parenchymal hematoma remote from infarcted brain tissue																																						
3b		Intraventricular hemorrhage																																						
3c		Subarachnoid hemorrhage																																						
3d		Subdural hemorrhage																																						
Investigator	Individual member of the investigation site team designated and supervised by the principal investigator at an investigation site to perform critical clinical-investigation-related procedures or to make important clinical investigation-related decisions.  Note 1: An individual member of the investigation site team can also be called “sub-investigator” or “co-investigator”.																																							
Investigator's Brochure (IB)	Compilation of the current clinical and non-clinical information on the investigational medical device(s), relevant to the clinical investigation.																																							

IV t-PA Failure	Failure of IV t-PA is defined as angiographic evidence of persistent target vessel occlusion 60 minutes or more after initiation of IV t-PA.																
Legally Authorized Representative (LAR)	Individual or judicial or other body authorized under applicable law to consent, on behalf of a prospective subject, to the subject's participation in the clinical investigation.																
Malfunction	Failure of an investigational medical device to perform in accordance with its intended purpose when used in accordance with the instructions for use or CIP																
Modified Rankin Score	
Measures the degree of disability or dependence in the daily activities of people who have suffered a stroke or other causes of neurological disability.
 
  
 Score	Description	
   
 0	No symptoms at all	
 
 1	No significant disability despite symptoms; able to carry out all usual duties and activities	
 
 2	Slight disability; unable to carry out all previous activities, but able to look after own affairs without assistance	
 
 3	Moderate disability; requiring some help, but able to walk without assistance	
 
 4	Moderately severe disability; unable to walk without assistance and unable to attend to own bodily needs without assistance	
 
 5	Severe disability; bedridden, incontinent and requiring constant nursing care and attention	
 
 6	Dead	
  
 
NOTE: Envi™-RCT will utilize the Rankin Focused Assessment—Ambulation (RFA-A) form which is based on mRS as described by van Swieten.
 
 
RFA-A reference:
 
	Score	Description	0	No symptoms at all	1	No significant disability despite symptoms; able to carry out all usual duties and activities	2	Slight disability; unable to carry out all previous activities, but able to look after own affairs without assistance	3	Moderate disability; requiring some help, but able to walk without assistance	4	Moderately severe disability; unable to walk without assistance and unable to attend to own bodily needs without assistance	5	Severe disability; bedridden, incontinent and requiring constant nursing care and attention	6	Dead
Score	Description																
0	No symptoms at all																
1	No significant disability despite symptoms; able to carry out all usual duties and activities																

Procedure Related Serious Adverse Events (PRSAE)	A serious adverse event where the interventional procedure caused, or cannot be ruled out as having caused, an effect that has resulted in any of the consequences characteristic of a serious adverse event. Consisting of: 
 
• Vascular perforation
 
• Intramural arterial dissection
 
• Embolization to a new territory
 
• Access site complication requiring surgical repair or blood transfusion
 
• Intra-procedural mortality
 
• Device failure (in-vivo breakage)
 
• Any other SAE adjudicated by the CEC to be related to the procedure
 

Procedure-related Mortality	The term utilized for death that occurs within a period of 7 days after the procedure or prior to discharge.
Protocol Deviation	Instance(s) of failure to follow, intentionally or unintentionally, the requirements of the Protocol.  Note 1: Includes Minor and Major  Note 2: Protocol Deviation(s) listed below are required to be reported to the EC/IRB/REB: 1. To protect the life or physical well-being of a subject in an emergency 2. If an investigator uses a device without obtaining informed consent
Recruitment	Active efforts to identify subjects who may be suitable for enrollment into the clinical investigation.
Serious Adverse Device Effect (SADE)	Adverse Device Effect that has resulted in any of the consequences characteristic of a Serious Adverse Event.
Serious Adverse Event (SAE)	Adverse event that 
 
a. Led to death,
 
b. Led to serious deterioration in the health of the subject, that either resulted in 
 
1. a life-threatening illness or injury, or
 
2. a permanent impairment of a body structure or a body function, or
 
3. in-patient or prolonged hospitalization, or
 
4. medical or surgical intervention to prevent life-threatening illness or injury or permanent impairment to a body structure or a body function
 
 
 
c. Led to fetal distress, fetal death or a congenital abnormality or birth defect
 

	Note 1: Planned hospitalization for a pre-existing condition, or a procedure required by the CIP, without serious deterioration in health, is not considered a serious adverse event.																									
Source Data	All information in original records, certified copies of original records of clinical findings, observations, or other activities in a clinical investigation, necessary for the reconstruction and evaluation of the clinical investigation.																									
Source Document	Printed, optical or electronic document containing source data.  EXAMPLES Hospital records, laboratory notes, device accountability records, photographic negatives, radiographs, records kept at the investigation site, at the laboratories and at the medico-technical departments involved in the clinical investigation.																									
Sponsor	Individual or organization taking responsibility and liability for the initiation or implementation of a clinical investigation.																									
Subject	Individual who participates in a clinical investigation.																									
Symptomatic ICH (sICH)	
Symptomatic ICH is a clinical event caused by intracranial hemorrhage. The determination of sICH involves an imaging and clinical adjudication per the Heidelberg Bleeding Classification. sICH to be reported as defined in Step 6: Definite and probable hemorrhage shall be classified as symptomatic.
 
  
 Step	Description	
   
 1	Brain Imaging	
 
 Scheduled according protocol within 48 h after treatment	
 
 Unscheduled triggered by symptoms suggestive of intracerebral hemorrhage	
 
 2	Independent and blinded review of imaging (i.e. Core Lab)	
 
 3	Anatomic description of intracranial hemorrhages (see ICH)	
 
 4	Adjudication of the cause of neurological deterioration in the presence of intracranial hemorrhage	
 
 4a	sICH: New intracranial hemorrhage detected by brain imaging associated with any of the item below:	
 
 ≥4 points total NIHSS at the time of diagnosis compared to immediately before worsening. Note that a 4 points change is not compared with the baseline admission NIHSS score but instead to the immediate pre-deterioration neurological status	
 
 ≥2 point in one NIHSS category. The rationale for this is to capture new hemorrhages that produce new neurological symptoms, making them clearly symptomatic but not causing worsening in the original stroke territory. For example, a new remote hemorrhage in the contralateral occipital lobe may cause new hemianopia that is clearly symptomatic but the patient will not have worsening of 4 points on the NIHSS score	
 
 Leading to intubation/hemicraniectomy/EVD placement or other major medical/surgical intervention.	
 
 Absence of alternative explanation for deterioration	
 
 4b	aICH: new hemorrhage that has no implications for prognosis or change in management, and there is no substantive change in the patient's neurological status	
 
 5	Establishing the relatedness of deterioration and imaging findings	
 
 In patients with neurological deterioration the relationship between clinical deterioration as defined in 4a and the hemorrhagic event is	
 
 Definite: if any intracranial hemorrhage is the dominant brain pathology on imaging causal for deterioration	
 
 Probable: in the presence of PH2, even if the ischemic infarct may have contributed to deterioration.	
  
	Step	Description	1	Brain Imaging	Scheduled according protocol within 48 h after treatment	Unscheduled triggered by symptoms suggestive of intracerebral hemorrhage	2	Independent and blinded review of imaging (i.e. Core Lab)	3	Anatomic description of intracranial hemorrhages (see ICH)	4	Adjudication of the cause of neurological deterioration in the presence of intracranial hemorrhage	4a	sICH: New intracranial hemorrhage detected by brain imaging associated with any of the item below:	≥4 points total NIHSS at the time of diagnosis compared to immediately before worsening. Note that a 4 points change is not compared with the baseline admission NIHSS score but instead to the immediate pre-deterioration neurological status	≥2 point in one NIHSS category. The rationale for this is to capture new hemorrhages that produce new neurological symptoms, making them clearly symptomatic but not causing worsening in the original stroke territory. For example, a new remote hemorrhage in the contralateral occipital lobe may cause new hemianopia that is clearly symptomatic but the patient will not have worsening of 4 points on the NIHSS score	Leading to intubation/hemicraniectomy/EVD placement or other major medical/surgical intervention.	Absence of alternative explanation for deterioration	4b	aICH: new hemorrhage that has no implications for prognosis or change in management, and there is no substantive change in the patient's neurological status	5	Establishing the relatedness of deterioration and imaging findings	In patients with neurological deterioration the relationship between clinical deterioration as defined in 4a and the hemorrhagic event is	Definite: if any intracranial hemorrhage is the dominant brain pathology on imaging causal for deterioration	Probable: in the presence of PH2, even if the ischemic infarct may have contributed to deterioration.
Step	Description																									
1	Brain Imaging																									
	Scheduled according protocol within 48 h after treatment																									
	Unscheduled triggered by symptoms suggestive of intracerebral hemorrhage																									
2	Independent and blinded review of imaging (i.e. Core Lab)																									
3	Anatomic description of intracranial hemorrhages (see ICH)																									
4	Adjudication of the cause of neurological deterioration in the presence of intracranial hemorrhage																									
4a	sICH: New intracranial hemorrhage detected by brain imaging associated with any of the item below:																									
	≥4 points total NIHSS at the time of diagnosis compared to immediately before worsening. Note that a 4 points change is not compared with the baseline admission NIHSS score but instead to the immediate pre-deterioration neurological status																									
	≥2 point in one NIHSS category. The rationale for this is to capture new hemorrhages that produce new neurological symptoms, making them clearly symptomatic but not causing worsening in the original stroke territory. For example, a new remote hemorrhage in the contralateral occipital lobe may cause new hemianopia that is clearly symptomatic but the patient will not have worsening of 4 points on the NIHSS score																									
	Leading to intubation/hemicraniectomy/EVD placement or other major medical/surgical intervention.																									
	Absence of alternative explanation for deterioration																									
4b	aICH: new hemorrhage that has no implications for prognosis or change in management, and there is no substantive change in the patient's neurological status																									
5	Establishing the relatedness of deterioration and imaging findings																									
	In patients with neurological deterioration the relationship between clinical deterioration as defined in 4a and the hemorrhagic event is																									
	Definite: if any intracranial hemorrhage is the dominant brain pathology on imaging causal for deterioration																									
	Probable: in the presence of PH2, even if the ischemic infarct may have contributed to deterioration.																									

		Possible: in the presence of HI2, PH1, rPH, IVH, SAH, SDH, even if ischemic infarct may have contributed predominantly to the deterioration
		Unlikely: in the presence of HI1
	6	Categories for trial or registry reporting
		Definite and probable: hemorrhage shall be classified as symptomatic
		Possible and unlikely: hemorrhage shall be classified as asymptomatic
	7	Adjudication of relatedness of intracranial hemorrhage (symptomatic and asymptomatic) to therapeutic intervention
		Relatedness is defined by
		Treatment with thrombolytic agents (IV or IA) within the last 24 h
		Area of hemorrhage compatible with endovascular complication (regional and temporal relationship)
		Documented complication of angiographic procedure
		Levels of certainty of relatedness
		Definite: observed procedural complication e.g., perforation of intracranial artery
		Probable: treatment within last 24 h. PH, symptomatic or asymptomatic
		Possible: treatment within last 24 h. HI, symptomatic, or asymptomatic
		Unrelated: no therapeutic intervention during the last 24 h before detection of hemorrhage
		Hemorrhage is spontaneous. Any anatomic type, symptomatic or asymptomatic
Thrombolysis in Cerebrovascular Infarction (TICI)	Not intended to be used, see reference. 	
Unanticipated Adverse Device Effect (UADE)	Any serious adverse effect on health or safety or any life-threatening problem or death caused by, or associated with, a device, if that effect, problem, or death was not previously identified in nature, severity, or degree of incidence in the investigational plan or application (including a supplementary plan or application), or any other unanticipated serious problem associated with a device that relates to the rights, safety, or welfare of subjects.	
	21CFR812.3	
Unanticipated Serious Adverse Device Effect (USADE)	Any serious adverse device effect which by its nature, incidence, severity or outcome has not been identified in the current version of the risk analysis report.	
	ISO 14155:2011	
Use Error	Act or omission of an act that results in a different medical device response than intended by the manufacturer or expected by the user.	
	Note 1: Use error includes slips, lapses, and mistakes.	
	Note 2: An unexpected physiological response of the subject does not in itself constitute a use error.	
	ISO 14971:2007	
Vulnerable Subject	A vulnerable subject is an Individual whose willingness to volunteer in a clinical investigation could be unduly influenced by the expectation, whether justified or not, of benefits associated with participation or of retaliatory response from senior members of a hierarchy in case of refusal to participate.	
	EXAMPLE Individuals with lack of or loss of autonomy due to immaturity or through mental disability, persons in nursing homes, children, impoverished persons, subjects in emergency situations, ethnic minority groups, homeless	

	persons, nomads, refugees, and those incapable of giving informed consent. Other vulnerable subjects include, for example, members of a group with a hierarchical structure such as university students, subordinate hospital and laboratory personnel, employees of the sponsor, members of the armed forces, and persons kept in detention.
--	---

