#### 3.1. Primary Endpoints

The primary effectiveness endpoint is the proportion of subjects with good clinical outcome defined as Modified Rankin Score (mRS) of  $\leq 2$  as assessed by a blinded assessor at 90 ( $\pm$  15) days post treatment.

The primary safety endpoint is the proportion of subjects with device-related or procedure-related symptomatic intracranial hemorrhage (sICH) at 24 hours (-8/+12 hours) post treatment defined by the Heidelberg Bleeding Classification as read by the Core Lab and adjudicated by the CEC.

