### 7.1. Cerebral CT or MR Imaging

This study will collect imaging data in line with routine practice as follows:

- Pre-procedure CT/ MRI
- 24-hour (-8/+12) CT/ MRI

All imaging should be in line with standard of care. No extra imaging should be performed for the purpose of the study. No patient should be exposed to extra radiation as a result of participation. It is preferred that the same imaging modality is used at 24 hour timepoint as at baseline (CT or MRI) to make direct comparison easier. MRI DWI is preferred, CT is acceptable.

Any other imaging performed (for example as a result of clinical deterioration) will also be provided.

In the event of abrupt neurologic deterioration or when deemed necessary by the investigator, an emergency CT or an MR imaging evaluation should be performed. An immediate evaluation of the presence/absence of hemorrhage, edema, and/or infarction as contributors to the clinical deterioration will be made. Any imaging taken prior to the routine 24-hour imaging (which may be taken in a time window of 16-36 hours without becoming a protocol deviation) for this reason will be included in the analysis.

Hemorrhages will be classified clinically and radiologically according to the Heidelberg Bleeding Classification (see definitions section for complete description).

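### The 24 h relatedness clock in Appendix A excludes symptomatic parenchymal hematomas first detected at 24 to 36 h from a primary safety endpoint whose window runs to 36 h

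*Combined protocol and SAP*

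**What the plan says.** Section 3.1 defines the primary safety endpoint as the proportion of subjects with "device-related or procedure-related symptomatic intracranial hemorrhage (sICH) at 24 hours (-8/+12 hours) post treatment defined by the Heidelberg Bleeding Classification". Section 7.1 gives the same limits for the routine scan, "which may be taken in a time window of 16-36 hours without becoming a protocol deviation".

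Appendix A, under device-related or procedure-related sICH, restricts the count to "sICH adjudicated by the CEC to be related to therapeutic intervention (either definite or probable) as defined by the Heidelberg Bleeding Classification".

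Appendix A, under symptomatic ICH, Step 7, sets the relatedness grades:

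- *Definite* requires an observed procedural complication and carries no time limit.
- *Probable*: "Probable: treatment within last 24 h. PH, symptomatic or asymptomatic".
- *Possible* covers hemorrhagic infarction (HI) with treatment in the last 24 h. It does not count towards the endpoint.
- *Unrelated*: "Unrelated: no therapeutic intervention during the last 24 h before detection of hemorrhage", followed by "Hemorrhage is spontaneous. Any anatomic type, symptomatic or asymptomatic".

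The Statistics section of the synopsis declares safety non-inferiority if the upper one-sided 97.5% bound for the difference in sICH is below 7 points. Section 3.4, safety endpoint 1, reports all post-procedure sICH with no relatedness filter.

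**The concern.** The endpoint window and the relatedness grade run on different clocks: one closes 36 h after treatment, the other looks back 24 h from detection. Between 24 and 36 h, a PH that meets every other condition cannot be graded *Probable*. If it is first found on the routine scan, it counts when that scan is at 23 h and not when it is at 25 h, although both scans comply with the protocol.

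A primary endpoint should not depend on when a site schedules its scan. The direction also matters. Losing the same fraction of events in both arms shrinks the absolute difference while the 7-point margin stays fixed, and this favours a finding of non-inferiority.

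**Working it through.** **Step 1: the window.** 24 - 8 = 16 h and 24 + 12 = 36 h. Endpoint and scan window agree on the upper limit.

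**Step 2: one case traced through Appendix A.** Take a PH2 with a 4-point NIHSS worsening, first detected at 30 h, with no complication seen during the procedure and no further intervention.

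- Step 4a: the worsening meets the sICH criterion.
- Steps 5 and 6: PH2 makes the link to deterioration at least probable, so the bleed is symptomatic.
- Section 3.1: 30 h is inside the window.
- Step 7: not *Definite* (no observed complication); not *Probable* (treatment was 30 h ago); it fits the 24 h line under *Unrelated*.
- Endpoint definition: not counted.

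Step 1 of the same table accepts scheduled imaging up to 48 h after treatment, so detection after 24 h is foreseen. I found no text that adapts the Step 7 clock to the 36 h window.

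**Step 3: which bleeds the clock changes.** Within 24 h, HI is at most *Possible* and SAH, IVH and SDH have no *Probable* row. The clock therefore changes the primary count only for PH without an observed complication.

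**Step 4: the plan's own figure.** Section 8.2 (Additional Estimates) gives 318 subjects for 4% in each arm, margin 7%, one-sided 2.5%, power 80%. Farrington-Manning, with restricted null rates of 9.47% and 2.47%:

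n per arm = [(1.960 × √(0.0947×0.9053 + 0.0247×0.9753) + 0.842 × √(2×0.04×0.96)) / 0.07]² = 158.96, rounded up to 159, or 318 in total. The stated figure is reproduced.

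**Step 5: effect on the 7-point test.** Inputs:

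- True related sICH in the 36 h window: 11% with Envi-SR and 4% with Control. The 4% is the planning ceiling in section 8.2; 11% = 4% + 7% puts the truth exactly at the margin.
- n per arm: 135 (270/2, target) and 224 (448/2, maximum ITT).
- f, the share of related sICH that the clock removes, assumed equal in both arms. The documents do not give it, so I show 0 to 40%.

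Observed rates become 11%(1 - f) and 4%(1 - f), and the difference 7(1 - f) points. The synopsis does not name the interval method for safety, so I use the Farrington-Manning score test, which matches the plan's sample size, and sum exactly over both binomial distributions. The last two columns give the probability of declaring non-inferiority.

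| f | Rates (%) | Difference (points) | 135/arm | 224/arm |
|---|---|---|---|---|
| 0 | 11.0 v 4.0 | 7.0 | 2.1% | 2.3% |
| 5% | 10.45 v 3.8 | 6.65 | 2.7% | 3.2% |
| 10% | 9.9 v 3.6 | 6.3 | 3.5% | 4.4% |
| 20% | 8.8 v 3.2 | 5.6 | 5.6% | 8.1% |
| 40% | 6.6 v 2.4 | 4.2 | 14.7% | 24.5% |

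A Newcombe bound gives similar values at f = 10%: 3.8% and 4.4%.

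In counts, at the planned 4% and 135 per arm, 135 × 0.04 = 5.4 events are expected per arm. With f = 10% this is 4.9, and with f = 20% it is 4.3.

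**The case against.** - **Judgement and ambiguity.** Step 7 first lists three criteria of relatedness, and only the thrombolytic one carries a 24 h limit; a regional and temporal fit with an endovascular complication does not. The remark that the bleed is spontaneous can be read as a further condition for *Unrelated*. The CEC has the final word (section 3.4), and its charter, cited in section 6.3, is not among these documents. This stands against saying that a late PH is *Unrelated* beyond dispute. It does not rescue the endpoint: the definition counts certainty levels, and a PH detected after 24 h still misses *Probable*.

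- **Symptomatic bleeds are mostly found early.** Section 7.1 asks for emergency imaging on abrupt deterioration and includes scans taken before the routine one. This stands. A reader might infer from 12 of the 20 scan-window hours lying beyond 24 h that 60% of events are at risk. That is a share of the routine scan window, not of events; the documents give no share of events.

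- **Scope.** A reader might also infer that every bleed after 24 h, of every type, drops out. The documents do not support this: *Definite* bleeds have no clock, bleeds detected within 24 h are kept, a further intervention restarts the clock, and non-PH types could not be *Probable* anyway.

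- **Error rate.** For the endpoint as literally defined, the test keeps its nominal level, and the table assumes a true Envi-SR rate of 11% where planning expects no more than 4%. Both are true. The inflation is relative to all related sICH in the stated 36 h window, which is what section 3.1 describes.

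- **Nothing goes unreported.** Safety endpoint 1 shows these events by arm. That is so, but the formal rule is not applied to it.

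**Conclusion.** The plan is wrong as written on a narrow point. A symptomatic PH first detected after 24 h and up to 36 h, with no observed procedural complication and no further intervention, falls inside the primary safety window and outside the primary safety count. This conclusion needs only the text of section 3.1, section 7.1 and the two Appendix A entries.

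The size is uncertain because f is not given. If f is 5 to 10%, the error relative to all related sICH in the window is 2.7 to 3.5% at 135 per arm and 3.2 to 4.4% at 224 per arm, against a nominal 2.5%. It becomes serious only if f reaches 20% or more. These figures assume a truth exactly at the margin and the same f in both arms. The sample size of 318 is not in question.

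**What to change.** Reconcile section 3.1, section 7.1 and the two Appendix A entries before adjudication begins; a later change would be open to challenge as post hoc.

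1. In the Appendix A definition of device-related or procedure-related sICH, and in the CEC instructions, state that for the primary safety endpoint the Step 7 treatment interval for the thrombectomy procedure (the *Probable* and *Unrelated* rows) runs from the index procedure to the end of the 36 h window. Leave the thrombolytic criterion and the rest of the classification unchanged.
2. Add all sICH detected to 36 h, regardless of relatedness, as a sensitivity analysis against the same 7-point margin. The data are already collected for safety endpoint 1.

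The cost is a definition edit, a CEC instruction and one extra table, with no new visits, scans or subjects. The observed sICH rate may be slightly higher, and the relatedness rule will depart slightly from the published classification, which should be stated in the report.
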